**Table 5: Operational Definition of Time 0 (index date) and other primary time anchors**

Study population name(s)	Time Anchor Description (e.g., time 0)	Number of entries	Type of entry	Washout window	Care Setting 	Code Type 	Diagnosis position	Incident with respect to...	Measurement characteristics / validation	Source of algorithm
All patients from the database eligible for the study and newly diagnosed with MDD	Patient present in the database during the study period (2013-2022) and with at least 1 year of valid database history, and no record MDD diagnosis in the previous year.	Single entry	Incident	[-365, ID]	IP and OP	n/a	n/a	MDD	n/a	n/a
All patients from the database eligible for the study – Analysis of incident antidepressant use in patients with newly diagnosed MDD	Patient present in the database during the study period (2013-2022) and with at least 1 year of valid database history.	Single entry	Incident	[-365, ID]	IP and OP	n/a	n/a	Specific drug class	n/a	n/a

ID = index date, IP = inpatient, OP = outpatient, n/a = not applicable, MDD = Major Depressive Disorder

	D2.2.3 –Study Protocol for P2 C1-008	
	Author(s): [name], [name]	Version: v3.0 – Revised
		Dissemination level: Confidential

## 8.5 Study Population with inclusion and exclusion criteria

### 8.5.1 Patient-level characterization of MDD treatment

The study cohort will comprise all patients, aged  $\geq 12$  years, with newly diagnosed MDD present in the respective databases during the study period (2013-2022) and with at least 365 days of data availability before the day they become eligible for study inclusion.

### 8.5.2 Patient-level utilization of antidepressants

All individuals aged 12 and above who are new users of antidepressants with incident MDD diagnosis, after 1 year of no use of the specific medication, in the period between 1st of January 2013 and 31st of December 2022 (or latest date available), with at least 1 year of data visibility prior to the date of their first prescription of the antidepressant class of interest.

	D2.2.3 –Study Protocol for P2 C1-008	
	Author(s): [name], [name]	Version: v3.0 – Revised
	Dissemination level: Confidential	

**Table 6. Operational Definitions of Inclusion Criteria**

Criterion	Details	Order of application	Assessment window	Care Settings 	Code Type	Diagnosis position 	Applied to study populations:	Measurement characteristics/ validation	Source for algorithm
Incident MDD	Patients with newly diagnosed MDD during the study period, that is individuals without a diagnosis of MDD 1 year prior.	After	1 year	IP, OP, OT	SNO MED	First	All study participants aged 12 years and above	N/A	N/A
Prior database history	Study participants will be required to have a year of prior history observed before contributing observation time	After	1 year	IP and OP	n/a	n/a	All patients, aged ≥ 12 years, with newly diagnosed MDD in the selected databases	n/a	n/a

 IP = inpatient, OP = outpatient, ED = emergency department, OT = other, n/a = not applicable

 Specify whether a diagnosis code is required to be in the primary position (main reason for encounter)

	D2.2.3 –Study Protocol for P2 C1-008	
	Author(s): [name], [name]	Version: v3.0 – Revised
	Dissemination level: Confidential	

## 8.6 Variables

### 8.6.1. Exposure

For this study, exposure of interest is use (during study period) of antidepressants and concomitant medications (psycholeptics). Exposure will be assessed at drug class level. The calculation of duration of the exposures is described in section 8.8.3 Statistical model specification and assumptions of the analytical approach considered.

The list of drug classes of interest is described in Table 7.

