### 8.2 Study Setting and Data Sources

This study will be conducted using routinely collected data from 5 databases in 4 European countries (3 EU countries and United Kingdom). All databases were previously mapped to the OMOP Common Data Model (CDM).

1. Clinical Practice Research Datalink GOLD (CPRD GOLD), United Kingdom
2. IQVIA Disease Analyzer Germany (IQVIA DA Germany), Germany
3. Institut Municipal Assistencia Sanitaria Information System (IMASIS), Spain (for this study, we will only use the outpatients)
4. Integrated Primary Care Information Project (IPCI), The Netherlands
5. The Information System for Research in Primary Care (SIDIAP), Spain

For this study, we selected 5 out of the 10 databases available in the DARWIN EU® Database Catalogue. The selection process was based on the size of the databases, the number of individuals with MDD and the counts of antidepressant class of interest across databases, as well as the geographical spread.

These selected databases fulfil the requirements for conducting both a patient-level characterisation study and a patient-level drug utilization study. This enables us to estimate the proportions of utilization related to treatment initiation, switching, and discontinuation for antidepressants in the context of incident MDD. Moreover, it facilitates the assessment of utilization proportions for treatment initiation, switching, and discontinuation of concomitant drug classes (specifically psycholeptics) within this patient cohort. Importantly, this selection encompasses databases from diverse clinical settings, thus allowing us to capture both inpatient and outpatient prescriptions or dispensing of drugs.

	D2.2.3 –Study Protocol for P2 C1-008	
	Author(s): [name], [name]	Version: v3.1 – Final
		Dissemination level: public

Additionally, these selected databases possess comprehensive data on MDD, along with representation of at least five ingredients from each of the three main antidepressant classes of interest. The rationale and justification for selecting these specific data sources, underpinned by their capacity to capture pertinent information, are detailed in **Table 4**.

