## 8.8 Data analysis

**Table 11.** Description of Study Types and Type of analysis

STUDY TYPE	STUDY CLASSIFICATION	TYPE OF ANALYSIS
Disease Epidemiology - Patient Level Characterisation	Off-the-shelf (C1)	
 
- Percentage of patients initiating treatment with specific antidepressants or psycholeptics
 
- Percentage of patients switching treatment to specific antidepressants or psycholeptics
 
- Percentage of patients discontinuing treatment with specific antidepressants or psycholeptics
 

Patient Level DUS	Off-the-shelf (C1)	
 
- Estimation of the mean, median, 25th percentile, 75th percentile, minimum, and maximum durations of antidepressant use.
 
- Estimation of the median, 25th percentile, 75th percentile, minimum, and maximum of the drug quantity at first prescription of the antidepressant of interest
 

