#### Patient-level characterisation: Treatment initiation, switching, and discontinuation

To characterise treatment of MDD, the number and percentages of patients receiving each of a pre-specified list of MDD treatments (as listed in section 8.6.1) will be described at index date, and 4, 6, 8, 12, and 24 weeks post index date. The criteria for treatment switching and discontinuation will be based on the options currently available in the standard analytical tools that will be used in this project, specifically, the “TreatmentPattern” R package. This analysis will produce sunburst plots and Sankey diagrams to describe treatment initiation, switching and discontinuation over time (objectives 1 and 3).

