**Figure 3. Parameters in TreatmentPatterns package (25)**

The following parameters will be defined in this study.

Parameters	Values (days)	Description
periodPriorToIndex	0	Number of days prior to the index date of the target cohort
minEraDuration	0	Minimum time an event era should last to be included in analysis
eraCollapseSize	7	Window of time between which two eras of the same event cohort are collapsed into one era
combinationWindow	7	Window of time two event cohorts need to overlap to be considered a combination treatment
minPostCombinationDuration	7	Minimum time an event era before or after a generated combination treatment should last to be included in analysis
filterTreatments	All	Select all treatments including first time occurrences and sequential repeated treatments
maxPathLength	5	Maximum number of steps included in treatment pathway

For all continuous variables, summary descriptive statistics will be reported: median and interquartile interval will be reported. For all categorical analyses, counts and percentages will be reported. A minimum cell count of 5 will be used when reporting results, with any smaller counts reported as “<5”. All analyses will be

	D2.2.3 –Study Protocol for P2 C1-008	
	Author(s): [name], [name]	Version: v3.1 – Final
		Dissemination level: public

reported by country/database, overall and stratified by age and sex when possible (minimum cell count reached).

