## APPENDIX I – LIST WITH PRELIMINARY CONCEPT DEFINITIONS FOR EXPOSURE

Prescriptions will be identified based on the relevant ingredient. Non-systemic products will be excluded from the code list.

CONCEPT ID	Name	ATC code
21604687	Non-selective monoamine reuptake inhibitors (NSRIs)	N06AA
21604709	Selective serotonin reuptake inhibitors (SSRIs)	N06AB
21604729	Other antidepressants (excluding N06AX25 and N06AX27)	N06AX
21604489	Psycholeptics	N05
21604490	Antipsychotics	N05A
21604564	Anxiolytics	N05B
21604606	Hypnotics and sedatives	N05C

	D2.2.3 –Study Protocol for P2 C1-008	
	Author(s): [name], [name]	Version: v3.1 – Final
		Dissemination level: public

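### Switching as planned counts only changes between drug classes, and with packs longer than 28 days many early between-class switches first appear as combination therapy

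*Protocol*

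**What the plan says.** Section 8.6.1 fixes the level of measurement: "Exposure will be assessed at drug class level". Table 7 lists three antidepressant and three psycholeptic classes. Section 8.2 reports "representation of at least five ingredients from each of the three main antidepressant classes of interest", so each antidepressant class leaves room for changes within it. Table 11 in section 8.8, however, promises "Percentage of patients switching treatment to specific antidepressants or psycholeptics", and Appendix I says "Prescriptions will be identified based on the relevant ingredient".

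Section 8.8.3 does not define a switch: "The criteria for treatment switching and discontinuation will be based on the options currently available in the standard analytical tools". Three settings in the parameter table under Figure 3 matter, each set to 7 days:
- eraCollapseSize: "Window of time between which two eras of the same event cohort are collapsed into one era"
- combinationWindow: "Window of time two event cohorts need to overlap to be considered a combination treatment"
- minPostCombinationDuration: "Minimum time an event era before or after a generated combination treatment should last to be included in analysis"

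Era lengths come from the start and end dates held in the drug exposure table (section 8.8.3), that is, from recorded supply. Switching is reported at 4, 6, 8, 12 and 24 weeks after initiation (section 8.6.2).

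**The concern.** The rationale (Abstract and section 6) asks whether intercurrent events seen in trials, among them a move to another therapy, occur as often in practice. That description is not limited to a change of class. If the reported proportion covers only changes between three broad classes, a reader who takes it as the switching rate will read it too low.

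The second issue is how supply-based eras interact with the overlap rule. A patient who stops class A mid-pack and starts class B still has A on record until the pack runs out. The overlap exists only on paper, but it can meet the 7-day criterion and be reported as combination use. Early timepoints would then show too little switching and too much combination therapy.

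Section 11 recognises that pack size distorts the proportion continuing treatment. It does not carry the argument over to switching, and it does not mention changes within a class. The only sensitivity analysis (section 8.8.4) concerns loss to follow-up.

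**Working it through.** The protocol states no switch rate, so there is no planned figure to reproduce. The check follows the settings through.

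**Within-class change.** The event cohorts are classes, so two ingredients of one class share a cohort.
- Gap of 7 days or less: eraCollapseSize merges the eras, and the record shows continued use.
- Gap above 7 days: the eras stay separate, and filterTreatments = All keeps repeats, so the record shows an interruption and then the same class again.
- In neither case is there a switch.

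If a share w of all drug changes is within class, class-level counting captures at most 1 − w. The documents do not give w. For assumed values of 20%, 40% and 60% the ceiling is 80%, 60% and 40%. This only restates the assumption and does not estimate the loss.

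**Mid-pack change between classes.** Inputs: combinationWindow = 7 (parameter table); pack P = 30 days (section 11 gives 30 pills at one a day as its example); other pack lengths are assumed. One pack of A starts at day 0. B starts on day d (1 to P − 1) and is then refilled, while A is not renewed. Switch days are assumed uniform.

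Recorded overlap = P − d. It is coded as combination if P − d ≥ 7, that is d ≤ P − 7. Share of mid-pack days = (P − 7)/(P − 1).

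| Pack (days) | Coded as combination |
|---|---|
| 28 (assumed) | 21/27 = 78% |
| 30 (protocol example) | 23/29 = 79% |
| 56 (assumed) | 49/55 = 89% |
| 60 (assumed) | 53/59 = 90% |
| 90 (assumed) | 83/89 = 93% |

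If the overlap must exceed 7 days, the 30-day figure is 22/29 = 76%.

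**What is counted at each timepoint.** There are two readings of the open switch rule. *Lenient*: A, then A+B, then B counts as a switch once A's supply has ended. *Direct*: only an immediate step from A to B counts. The denominator is the number of switch days up to the timepoint.

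| Pack | Timepoint | Lenient | Direct |
|---|---|---|---|
| 28 | week 4 | 27/27 | 6/27 |
| 30 | week 4 (day 28) | 5/28 | 5/28 |
| 30 | week 6 onward | 29/29 | 6/29 |
| 60 | week 8 | 3/56 | 3/56 |
| 60 | week 12 onward | 59/59 | 6/59 |
| 90 | week 12 | 1/84 | 1/84 |
| 90 | week 24 | 89/89 | 6/89 |

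For the 30-day pack at week 4, only d = 24 to 28 leaves an overlap below 7 days, hence 5 of 28. The lenient reading recovers a switch only once A's pack has run out. The loss is therefore certain at every timepoint that falls before the end of the pack, and beyond that it depends on the rule chosen.

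**The case against.** Class level is the declared target. The objectives, section 8.1 and Tables 7 and 8 all speak of classes, and Objective 2 measures duration of the first episode of a class. This stands: a between-class proportion is a correct answer to the objectives as worded. A reader might infer that duration and discontinuation are therefore biased in a favourable direction. The documents do not support that, because those quantities are defined at class level and no trial definition or trial rate is given for comparison.

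A reader might also infer that every within-class change looks like unbroken treatment. That holds only for gaps of 7 days or less.

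The strongest technical objection is that minPostCombinationDuration = 7 keeps B visible after the combination, so a switch may be delayed and not lost. This also stands. A general claim of permanent under-counting is not supported; it depends on a rule that section 8.8.3 leaves to the package and that an analysis plan not at hand may settle. With a 28-day pack, the lenient reading loses nothing even at week 4.

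Section 11 concedes that prescribed duration may differ from actual use, and it promises initial quantities by antidepressant and database. That helps with context, but it does not mention switching.

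**Conclusion.** The point holds in two parts.

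First, the outcome is between-class switching only. It is narrower than the research question, sits awkwardly with Table 11's wording and is not listed as a limitation. The direction relative to all drug changes is downward; the size cannot be computed from the documents.

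Second, supply-based eras with a 7-day overlap rule first code 79% of mid-pack between-class switch days as combination for the protocol's example pack. These are missed at week 4 on any reading, and for longer with longer packs: through week 8 at 60 days and through week 12 at 90 days. From week 6 with a 30-day pack the loss is either nil or 23 of 29, depending on how A, A+B, B is classified.

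The percentages assume uniform switch days and a single unrenewed pack of A. Switches made at refill are affected less, and neither their share nor the distribution of pack sizes is given. The figures describe the mechanism and do not predict the error in the reported proportions. The point deserves correction before the code is run, but it does not undermine the class-level objectives.

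**What to change.** 1. Keep the class-level analysis, but label the outcome *between-class switching* throughout. For Objective 1, add an ingredient-level run, overall only and not stratified by age or sex, that reports within-class and between-class switches separately.
2. State whether A, then A+B, then B counts as a switch, and on which date. Beside the package output, add one sensitivity analysis. One option is to count that sequence as a switch dated at B's start when A is not renewed. The other is to vary combinationWindow, for example 7 versus 30 days. With a 30-day pack the largest mid-pack overlap is 29 days, so a 30-day window would code none of these as combination; with a 90-day pack it would still code 60 of 89 (d ≤ 60).
3. Reconcile section 8.6.1 with Table 11, and add both effects to section 11.

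Cost: one extra cohort set, some custom code and more cells below 5. Appendix I already identifies prescriptions by ingredient, and section 8.8.4 already accepts an overall-only analysis where the package cannot produce it. The non-renewal rule has its own error: true add-on therapy with a long pack of A that is not renewed may be read as a switch, and status at an early timepoint then depends on later prescriptions. It therefore belongs in a sensitivity analysis and should not replace the main one.

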**Table 7: Exposure of interest**

Drug Class of interest	ATC code
I. Main drugs of interest (antidepressants)	
Non-selective monoamine reuptake inhibitors (NSRIs)	N06AA
Selective serotonin reuptake inhibitors (SSRIs)	N06AB
Other Antidepressants (excluding N06AX25 and N06AX27)	N06AX
II. Concomitant drugs of interest (psycholeptics)	
Antipsychotics	N05A
Anxiolytics	N05B
Hypnotics and sedatives	N05C

Details of exposure are described in Table 8.

	D2.2.3 –Study Protocol for P2 C1-008	
	Author(s): [name], [name]	Version: v3.0 – Revised
	Dissemination level: Confidential	

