### Variables

#### *Drug class of interest:*

- Non-selective monoamine reuptake inhibitors
- Selective serotonin reuptake inhibitors
- Other antidepressants (excluding esketamine and Hyperici herba)
- Concomitant medications – Psycholeptics
  - ✓ Antipsychotics
  - ✓ Anxiolytics
  - ✓ Hypnotics and sedatives

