Despite the available treatments, a considerable proportion of MDD patients, estimated at 10% to 30%, exhibit limited or no response to medications, highlighting the need for novel therapeutic approaches. (10) Clinical trials (CTs) play a crucial role in evaluating treatment efficacy and safety but understanding intercurrent events (IEs) occurring after starting therapy is essential for translating CT findings to real-life clinical practice. (11) IEs, events that arise after treatment initiation and impact the interpretation of outcomes, can include treatment discontinuation, switches to alternative therapies, and modifications in concomitant treatments, introducing complexity in the definition and the estimation of a treatment effect. (11-13) Addressing IEs in CTs requires the definition of a target estimand. Where such estimands include strategies defined as treatment policy (considering the outcomes regardless of the occurrence of IEs) or composite (as a signal of treatment failure), their incidence in the trial is a determinant of the treatment effect estimated, raising a question around the external validity of such estimate.

This study aims to provide valuable insights into the incidence in clinical practice of such events, and in particular of treatment discontinuation, initiation of (other) treatments, and switching among newly diagnosed MDD patients prescribed antidepressants and psycholeptics in various European clinical settings. Understanding the impact of IEs in real-life clinical practice will facilitate extrapolation of CT findings to improve everyday patient care and outcomes in MDD management.

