### **Study objectives**

1. To examine the proportion of patients with newly diagnosed major depressive disorder who start treatment with antidepressants (NSRIs, SSRIs, or other anti-depressants), as well as those who switch or discontinue treatment by specific timepoints (4, 6, 8, 12, and 24 weeks after treatment initiation), stratified by age, sex, and country/database during the study period (2013 - 2022).
2. To estimate the duration of antidepressant use in patients with newly diagnosed major depressive disorder who initiate treatment with antidepressants (NSRIs, SSRIs, or other antidepressants), stratified by age, sex, and country/database during the study period (2013 - 2022).
3. To assess the proportions of patients with newly diagnosed major depressive disorder who initiate, switch, or discontinue treatment with psycholeptics (antipsychotics, anxiolytics, hypnotics, and sedatives) by specific timepoints (4, 6, 8, 12, and 24 weeks) after starting antidepressant therapy, stratified by age, sex, and country/database during the study period (2013 - 2022).

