### 8.4 Follow-up

Patient-level characterisation: study participants will be followed from the date of MDD diagnosis (index date) until the earliest of loss to follow-up, end of data availability, death, or end of study period (31st December 2022). Additionally:

- To assess the proportions of patients with newly diagnosed MDD initiating antidepressant therapy, incident MDD cases will be followed from the date of MDD diagnosis (index date) until the first prescription of the antidepressant class of interest, up to 24 weeks following MDD diagnosis.
- To assess the proportions of patients with newly diagnosed MDD switching or discontinuing specific antidepressant therapy, incident MDD cases on antidepressant therapy will be followed from the date of the first prescription of the specific antidepressant class of interest up to the date of specific intervals (4, 6, 8, 12, and 24 weeks) after starting antidepressant therapy.
- To assess the proportions of patients with newly diagnosed MDD starting, switching and discontinuing concomitant therapy with psycholeptics, incident MDD cases on antidepressant therapy will be followed from the date of the first prescription of the specific antidepressant class of interest up to the date of specific intervals (4, 6, 8, 12, and 24 weeks) after starting antidepressant therapy.

Patient-level utilization of antidepressants: study participants will be followed up from the date of incident prescription and/or dispensation of antidepressant class of interest (index date) until the earliest of loss to follow-up, end of data availability, death, or end of study period (31st December 2022).

	D2.2.3 –Study Protocol for P2 C1-008	
	Author(s): [name], [name]	Version: v3.0 – Revised
	Dissemination level: Confidential	

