### 8.6.2. Outcomes

This study will examine the following four primary outcomes of interest.

- Treatment Initiation

Initiation of treatments will be assessed within a window of 4, 6, 8, 12, and 24 weeks following diagnosis. In relation to the outcome, a predefined list of MDD treatments will be compiled to address Objectives 1 and 3. MDD treatments will include NSRIs, SSRIs, other antidepressants, and concomitant drugs of interest (Psycholeptics - N05A, N05B, and N05C) as listed in Table 7.

- Treatment Switching

Switching of treatments will be assessed within a window of 4, 6, 8, 12, and 24 weeks following treatment initiation. In relation to the outcome, a predefined list of MDD treatments will be compiled to address Objectives 1 and 3. MDD treatments will include NSRIs, SSRIs, other antidepressants, and concomitant drugs of interest (Psycholeptics - N05A, N05B, and N05C) as listed in Table 7.

- Treatment Discontinuation

Discontinuation of treatments will be assessed within a window of 4, 6, 8, 12, and 24 weeks following treatment initiation. In relation to the outcome, a predefined list of MDD treatments will be compiled to address Objectives 1 and 3. MDD treatments will include NSRIs, SSRIs, other antidepressants, and concomitant drugs of interest (Psycholeptics - N05A, N05B, and N05C) as listed in Table 7.

	D2.2.3 –Study Protocol for P2 C1-008	
	Author(s): [name], [name]	Version: v3.0 – Revised
	Dissemination level: Confidential	

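### A move to an antidepressant outside Table 7 cannot be counted as a switch and will look like stopping treatment

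*Protocol*

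**What the plan says.** Table 7 (Protocol section 8.6.1) lists three antidepressant classes: N06AA, N06AB and "Other Antidepressants (excluding N06AX25 and N06AX27". The abstract names the two exclusions as products: "Other antidepressants (excluding esketamine and Hyperici herba". Appendix I repeats the three classes and the exclusions. None of these places gives a reason.

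Section 8.6.2 uses the same statement for initiation, switching and discontinuation: "MDD treatments will include NSRIs, SSRIs, other antidepressants, and concomitant drugs of interest (Psycholeptics - N05A, N05B, and N05C) as listed in Table 7". Table 9 points each of the three outcomes to the Table 7 codes.

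The rule that turns eras into outcomes is not written out. Section 8.8.3 says: "The criteria for treatment switching and discontinuation will be based on the options currently available in the standard analytical tools". Section 8.4 describes the group followed as "patients with newly diagnosed MDD switching or discontinuing specific antidepressant therapy".

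Section 6 explains why the distinction matters. It names the intercurrent events of interest in trials as "treatment discontinuation, switches to alternative therapies, and modifications in concomitant treatments". It then gives discontinuation, start of other treatments and switching as what this study will measure in practice.

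**The concern.** Discontinuation and switching are separate intercurrent events, and the study exists to give a rate for each. A pathway built only from listed classes cannot see a drug for which no event cohort exists. A patient who leaves an SSRI for one of the two excluded products therefore produces the same record as a patient who leaves an SSRI for nothing.

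These patients leave the switching count and enter the discontinuation count. The misclassification does not cancel out, because no patient is moved the other way by the same mechanism. A reader comparing these rates with a trial that recorded such moves as switches would see a difference that comes partly from the code list.

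**Working it through.** **1. Is the list closed?** The antidepressant entries in Table 7 and Appendix I are the same three classes with the same two exclusions. Table 9 takes all three outcomes from Table 7. No further antidepressant category is defined.

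**2. Does anything recover a drug outside the list?**
- The parameters set for TreatmentPatterns in section 8.8.3 (era collapse 7 days, combination window 7 days, post-combination minimum 7 days, path length 5, and the others) act on event cohorts that already exist. None creates a new one.
- The sensitivity analysis in section 8.8.4 deals with loss to follow-up only.
- Section 11 covers diagnosis accuracy, incomplete recording, assumed durations, loss to follow-up and pack size. It does not cover moves to antidepressants outside the list.

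**3. How would different patients be read by a given timepoint?** All start an SSRI.

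| Course | What the list shows | Reading |
|---|---|---|
| SSRI ends, a listed class starts | a second antidepressant event | switch |
| SSRI ends, nothing starts | no later antidepressant event | stop |
| SSRI ends, N06AX25 or N06AX27 starts | no later antidepressant event | stop |
| SSRI continues, N06AX25 or N06AX27 is added | SSRI era continues | neither; no false stop |
| SSRI ends, N06AX25 or N06AX27 starts, a listed psycholeptic continues | psycholeptic event only | depends on the package rule, which the protocol does not state |

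Rows two and three cannot be told apart. Row three is the error; rows four and five limit it.

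**4. Size.** The protocol states no figure to reproduce: no power, no calculated sample size, and no frequency of use for drugs outside the list. A bound can still be written. Let *m* be the share of initiators who end a listed era and move to an antidepressant outside the list by the timepoint. Let *D* and *S* be the true discontinuation and switching proportions. Then

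- observed discontinuation ≤ *D* + *m*
- observed switching ≥ *S* − *m*

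These are bounds because some such patients stay on a listed drug, have already switched between listed classes, or still show a psycholeptic event.

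Illustration at the bound, with every input assumed: *D* = 40%, *S* = 10%, *m* from 0.1% to 5%.

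| *m* | Observed discontinuation | Relative excess (*m*/40) | Observed switching | Relative shortfall (*m*/10) |
|---|---|---|---|---|
| 0.1% | 40.1% | 0.25% | 9.9% | 1% |
| 0.5% | 40.5% | 1.25% | 9.5% | 5% |
| 1% | 41% | 2.5% | 9% | 10% |
| 3% | 43% | 7.5% | 7% | 30% |
| 5% | 45% | 12.5% | 5% | 50% |

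With *D* = 20%, the relative excess at *m* = 1% is 1/20 = 5%. With *D* = 60% it is 1/60 = 1.67%. For a given *m*, the smaller proportion is distorted more in relative terms. If switching is much rarer than discontinuation, as assumed here, it is the figure more exposed.

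**The case against.** The strongest reply is that the scope is declared. The objectives name the classes ("start treatment with antidepressants (NSRIs, SSRIs, or other anti-depressants"), and the exclusions are stated in the abstract, Table 2, Table 7 and Appendix I. Any closed code list has an edge: section 6 mentions psychotherapy and electroconvulsive therapy, and a move to either would also look like stopping. Table 7 is described elsewhere as a preliminary code list. The trial-level description of switching in section 6 concerns intercurrent events in general, not this study's own definition.

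Much of this stands, and it rules out four stronger readings that a reader might infer:

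- *That the protocol defines discontinuation as leaving the three antidepressant groups.* It does not. The criteria are left to the package, the outcome list includes psycholeptics, and section 8.4 follows the specific class. Only the consequence holds: a drug without an event cohort cannot be the target of a switch.
- *That initiation is undercounted.* Section 8.4 follows patients to a first prescription of a class of interest. A patient who starts only an excluded product is correctly not an initiator under that definition.
- *That other antidepressant subclasses are known to be missing.* The protocol names only N06AX25 and N06AX27 as excluded. Section 8.2 calls the three classes the main ones, which hints at others but identifies none.
- *That differences between databases are distorted.* This would need use of the excluded products to differ by country or setting, and the documents do not show that it does.

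Declared scope does not answer the remaining point. Declaring which drugs are studied settles who enters as an initiator. It does not make a move to another antidepressant a stop. Such a move falls within drug treatment, where the study sets out to separate switching from stopping, and section 11 does not disclose it.

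**Conclusion.** The point holds for switching against discontinuation only. With event cohorts built solely from Table 7, a patient who ends a listed antidepressant era and moves to N06AX25, N06AX27 or another antidepressant outside the list cannot be counted as switching and will appear to have stopped. A concurrent listed psycholeptic may alter the reading, depending on a rule the protocol leaves to the package. An add-on to a continuing listed drug creates no false stop.

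The direction is certain; the size is not. The bound equals the share of initiators making such a move, and the documents give no value for it. The 0.1% to 5% range, the 40% and the 10% are assumptions for illustration. The true share may be small. This is a low-severity improvement and does not threaten the study's main results.

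**What to change.** Keep the drugs of interest as they are. Add one auxiliary event cohort for antidepressants outside Table 7, covering at least N06AX25 and N06AX27, and use it only to classify how a listed era ends. Report a listed era followed by this cohort in a separate row, as a switch to a non-study antidepressant, and not under discontinuation. Leave the initiation outcome unchanged.

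State three things alongside it: the rule for discontinuation and switching in words, including how a continuing psycholeptic is treated; the reason for the two exclusions; and how overlap with a listed era is handled, so that the auxiliary cohort does not itself create combination steps under the 7-day window.

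The cost is one more concept set and one more row per table. Some cells will be small and masked under the existing rule for counts below 5. Capture of non-prescription products will be incomplete, so some moves will still look like stopping; section 11 should say so.
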